15.2. Publications by Investigators

Pfizer supports the exercise of academic freedom and has no objection to publication by the principal investigator (PI) of the results of the study based on information collected or generated by the PI, whether or not the results are favorable to the Pfizer product. However, to ensure against inadvertent disclosure of confidential information or unprotected inventions, the investigator will provide Pfizer an opportunity to review any proposed

publication or other type of disclosure of the results of the study (collectively, "publication") before it is submitted or otherwise disclosed.

The investigator will provide any publication to Pfizer at least 30 days before it is submitted for publication or otherwise disclosed. If any patent action is required to protect intellectual property rights, the investigator agrees to delay the disclosure for a period not to exceed an additional 60 days.

The investigator will, on request, remove any previously undisclosed confidential information before disclosure, except for any study- or Pfizer product-related information necessary to the appropriate scientific presentation or understanding of the study results.

If the study is part of a multicenter study, the investigator agrees that the first publication is to be a joint publication covering all investigator sites, and that any subsequent publications by the PI will reference that primary publication. However, if a joint manuscript has not been submitted for publication within 12 months of completion or termination of the study at all participating sites, the investigator is free to publish separately, subject to the other requirements of this section.

For all publications relating to the study, the institution will comply with recognized ethical standards concerning publications and authorship, including Section II - "Ethical Considerations in the Conduct and Reporting of Research" of the Uniform Requirements for Manuscripts Submitted to Biomedical Journals, http://www.icmje.org/index.html#authorship, established by the International Committee of Medical Journal Editors.

Publication of study results is also provided for in the CSA between Pfizer and the institution. In this section entitled Publications by Investigators, the defined terms shall have the meanings given to them in the CSA.

If there is any conflict between the CSA and any attachments to it, the terms of the CSA control. If there is any conflict between this protocol and the CSA, this protocol will control as to any issue regarding treatment of study subjects, and the CSA will control as to all other issues.

Appendix 1. Abbreviations

This following is a list of abbreviations that may be used in the protocol.

Abbreviation	Term
AD	atopic dermatitis
AE	adverse event
ALT	alanine aminotransferase
AST	aspartate aminotransferase
ATP	adenosine triphosphate
AUC	Area under the curve
AUC _{inf}	area under the curve from time zero extrapolated to infinity
AUC _{last}	area under the curve from time zero to last quantifiable
AUC _{tau}	area under the curve over dosing interval tau
BBS	Biospecimen Banking System
BCG	Bacille Calmette Guérin
BID	twice a day
BP	blood pressure
BSA	body surface area
C _{max}	peak plasma concentration
CD	cluster of differentiation
CFB	change from baseline
CFR	Code of Federal Regulations
CI	confidence interval
CL/F	clearance/fraction of dose absorbed
CO2	carbon dioxide
CK	creatine kinase
СМН	Cochran-Mantel-Haenszel
CNIL	French Data Protection Authority
CRF	case report form
CSA	clinical study agreement
CsA	cyclosporine A
CS	clinically significant
CSF	cerebrospinal fluid
CSR	clinical study report
C-SSRS	Columbia Suicide Severity Rating Scale
CT	clinical trial
CTA	clinical trial application
CTCAE	Common Terminology Criteria for Adverse Events
CV	Coefficient of variation
DCT	Data Collection Tool
DILI	drug-induced liver injury
DLQI	Dermatology Life Quality Index
DMC	data monitoring committee

Abbreviation	Term
DNA	deoxyribonucleic acid
DU	dispensable unit
EASI	Eczema Area and Severity Index
EBV	Epstein Barr virus
EC	ethics committee
ECG	electrocardiogram
eCRF	electronic Case Report Form
e-Diary	electronic diary
E-DMC	external data monitoring committee
EDP	exposure during pregnancy
ELISA	Enzyme-Linked Immunosorbent Assay
EMA	European Medicines Agency
EOS	end of study
EOT	end of treatment
EPO	erythropoietin
EQ-5D-5L	EuroQol Quality of Life 5-Dimension 5-Level Scale
ET	early termination
EU	European Union
EudraCT	European Clinical Trials Database
FACS	fluorescence-activated cell sorting
FAS	full analysis set
FDA	Food and Drug Administration
FSH	follicle-stimulating hormone
GCP	Good Clinical Practice
GGT	Gamma-glutamyl transferase
GM-CSF	granulocyte-macrophage colony-stimulating factor
HADS	Hospital Anxiety and Depression Scale
HADS	Hospital Anxiety and Depression Scale
HBsAb	hepatitis B surface antibody
HBsAg	hepatitis B surface antigen
HBcAb	hepatitis B core antibody
HBV	hepatitis B virus
HBV DNA	hepatitis B virus deoxyribonucleic acid
CCI	
HCV	hepatitis C virus
HCVAb	hepatitis C antibody
HCV RNA	hepatitis C viral ribonucleic acid
HDL	high-density lipoprotein
HEENT	head, eyes, ears, nose and throat
HIV	human immunodeficiency virus
HRQL	health-related quality of life
CCI	
HSV	herpes simplex virus

Abbreviation	Term
HTA	health technologies assessment
IB	Investigator's Brochure
ICH	International Council for Harmonisation
ID	identification
IFN	interferon
IFN-α	interferon-alpha
IFN-γ	interferon-gamma
IGA	Investigator's Global Assessment
IgE	Immunoglobulin E
IgG	immunoglobulin G
IIV	inter individual variability
IL	interleukin
IND	investigational new drug application
INR	international normalized ratio
IP	investigational product
IRB	institutional review board
IRC	internal review committee
IRT	interactive response technology
ITT	intent to treat
IUD	intrauterine device
IWR	interactive web response
JAK	Janus kinase
JAK1	Janus kinase 1
CCI	
LDL	low-density lipoprotein
LFT	liver function test
LLQ	lower limit of quantification
LSLV	last subject last visit
LTE	long-term extension
MAA	marketing authorisation application
MAR	missing at random
MCH	mean corpuscular hemoglobin
MCHC	mean corpuscular hemoglobin concentration
MCV	mean corpuscular volume
MMRM	mixed-effect model with repeated measures
MNAR	missing not at random
MnB	meningitidis serogroup B
MRI	magnetic resonance imaging
MTX	methotrexate
N/A	not applicable
NB-UVB	narrowband ultraviolet B light
OTC	over the counter

Abbreviation	Term
Pruritus NRS4	improvement in the severity of Pruritus NRS from baseline by at
	least 4 points
NRS	numerical rating scale
PCD	primary completion date
PCP	primary care physician
PD	Pharmacodynamics
PEER Study	Pediatric Eczema Elective Registry Study
PFS	prefilled syringe
PGIC	Patient Global Impression of Change
PGIS	Patient Global Impression of Severity
PGx	Pharmacogenomics
PHQ-8	Patient Health Questionnaire - 8 items
PI	principal investigator
PK	Pharmacokinetics
POC	proof of concept
POEM	Patient-Oriented Eczema Measure
PPAS	per-protocol analysis set
PPD	purified protein derivative test
PRO	patient reported outcome
PSAAD	Pruritus and Symptoms Assessment for Atopic Dermatitis
PT	prothrombin time
PtGA	Patient Global Assessment
QD	once daily
QFT-G	QuantiFERON®-TB Gold
QT	Q wave interval
QTc	corrected Q wave interval
QTcF	Fridericia corrected Q wave interval
R _{ac}	accumulation ratio
RBC	red blood cell
RNA	ribonucleic acid
SAE	serious adverse event
SAP	statistical analysis plan
SCORAD	SCORing atopic dermatitis
SOC	system organ class
SOP	standard operating procedure
SRSD	single reference safety document
STAT	signal transducers and activators of transcription
SUSAR	suspected unexpected serious adverse reaction
t _{1/2}	Half-life
TARC	thymus and activation regulated chemokine
TB	tuberculosis
TBili	total bilirubin
TCI	topical calcineurin inhibitors

Abbreviation	Term
TCS	topical corticosteroids
TdP	Torsade de Pointes
TH1	type 1 helper T cell
TH2	type 2 helper T cell
T_{max}	time to maximum absorption
TPO	Thrombopoietin
TYK2	tyrosine kinase 2
ULN	upper limit of normal
US	United States
USPI	United States Package Insert
UVA	ultraviolet A light
UVB	ultraviolet B light
VAS	visual analog scale
V/F	volume of distribution/fraction absorbed
VZV	varicella zoster virus
CCI	
WBC	white blood cell
WOCBP	woman of childbearing potential
WONCBP	women of non-childbearing potential

Appendix 2. Diagnostic Criteria for Atopic Dermatitis

Per Inclusion Criterion 3, a subject is to have a clinical diagnosis of atopic dermatitis according to the criteria of Hanifin and Rajka. ¹⁷

Hanifin and Rajka's Diagnostic Criteria for Atopic Dermatitis

Must have three or more basic features described below:

Pruritus

Typical morphology and distribution:

Flexural lichenification in adults

Facial and extensor eruptions in infants and children

Chronic or chronically-relapsing dermatitis

Personal or family history of atopy (asthma, allergic rhinitis, atopic dermatitis)

Must have three or more following minor features:

Xerosis

Ichthyosis/palmar hyperlinearity, keratosis pilaris

Immediate (type 1) skin test reaction

Elevated serum IgE

Early age of onset

Tendency toward cutaneous infections (esp. staph. aureus and herpes simplex), impaired cell-mediated immunity

Tendency toward non-specific hand or foot dermatitis

Nipple eczema

Cheilitis

Recurrent conjunctivitis

Dennie-Morgan infraorbital fold

Keratoconus

Anterior subcapsular cataracts

Orbital darkening

Facial pallor, facial erythema

Pityriasis alba

Anterior neck folds

Itch when sweating

Intolerance to wool and lipid solvents

Periofollicular accentuation

Food intolerance

Course influenced by environmental and emotional factors

White dermographism, delayed blanch

Appendix 3. Prohibited Concomitant Medications

CYP2C19 Inhibitors

Fluconazole (Diflucan)
Fluvoxamine (Luvox)
Ticlopidine (Ticlid)
Esomeprazole (Nexium)
Fluoxetine (Prozac)
Moclobemide
Omeprazole (Prilosec)
Voriconazole (Vfend)

CYP2C19 Inducers

Enzalutamide (Xtandi) Rifampin

CYP2C9 Inhibitors

Fluconazole (Diflucan)
Amiodarone (Cordarone)
Fluvoxamine (Luvox)
Miconazole
Oxandrolone (Oxandrin)
Voriconazole (Vfend)

CYP2C9 Inducers

Carbamazepine (Tegretol) Enzalutamide (Xtandi) Rifampin

Note 1: All CYP2C9 and CYP2C19 inhibitors require at least 1 week or at least 5 half-lives (whichever is longer) washout period prior to the first dose of investigational product.

Note 2: All CYP2C9 and CYP2C19 inducers require a period of washout of at least 5 half-lives plus 14 days prior to the first dose of investigational product. For example, the average half-life of Carbamazepine after repeat dosing is 15 hours. The washout period is calculated as the sum of 5 half-lives (approximately 3 days) and an additional 14 days for a total of 17 days prior to the first dose of investigational product.

Note 3: Half-life refers to the half-life of the parent drug and its metabolites, which are inhibitors or inducers. The longest half-life should be used to calculate the period necessary to washout a medication prior to the first dose of investigational product. For example, fluoxetine and its metabolite norfluoxetine are both inhibitors of CYP2C19. The terminal half-life of fluoxetine is up to 6 days. However, norfluoxetine has a longer half-life, up to 16 days. Therefore, the washout period should be calculated based on the 5 times the half-life of norfluoxetine, for a total of approximately 80 days prior to the first dose of investigational product.

This is not an all-inclusive list. Study personnel should stay current and consult with their pharmacy to exclude all concomitant medications that are CYP2C9 or CYP2C19 inhibitors or inducers.

Appendix 4. Monitoring and Discontinuation Criteria

Monitoring Criteria

The following laboratory abnormalities require prompt retesting:

- Neutrophil counts <1000 neutrophils/mm³; confirmed promptly by repeat testing, ideally within 3-5 days;
- Platelet counts <75,000 platelets/mm³; confirmed promptly by repeat testing, ideally within 3-5 days;
- Any single hemoglobin value <9.0 g/dL or one that drops ≥2 g/dL below baseline; confirmed promptly by repeat testing, ideally within 3-5 days;
- Any single AST and/or ALT elevation >3 times the upper limit of normal regardless
 of accompanying symptoms or the total Bilirubin should prompt repeat testing. This
 should also prompt review of Section 8.4.2; additional investigations must be
 conducted.

Temporary Interruption to Dosing

An investigator can temporarily interrupt dosing for up to a maximum of 14 consecutive days for a subject, for safety reasons or while monitoring abnormal laboratory tests if the investigator judges that this is necessary. In the case of investigational product being withheld, all investigational products that the subject is receiving should be withheld (ie, both oral and injected investigational product, as applicable). The investigator should use their judgement with regard to unscheduled visits/laboratory/clinical assessments required to monitor the subject during this timeframe. If within this timeframe the investigator judges that it is safe to restart dosing, then the subject may restart investigational product. If the investigator judges that it is not safe to restart dosing within this timeframe then the subject must be permanently discontinued from treatment, have an End of Treatment visit and enter the 4-week follow-up period. Doses not taken for the reasons mentioned above do not constitute protocol deviations or medication errors and should not be considered dosing errors, but should be noted in the dosing log with the reason for reduced drug consumption clearly described.

Discontinuation Criteria

Subjects must be permanently discontinued from treatment if they meet any of the following criteria at any point in the study:

- Marked prolongation of the QTcF interval to >500 ms or >60 ms change from screening ECG.
- Serious infection (see definition for Serious Adverse Events in Section 8.2.3).

- Any bleeding event thought to be associated with a platelet count reduction per the judgement of the investigator (or, if necessary/desired, following discussion with sponsor).
- Adverse event, per judgment of the investigator, requiring discontinuation from treatment (or, if necessary/desired, following discussion with sponsor).
- Any adverse event or laboratory abnormality, that per the investigator's judgement requires withholding of investigational product for >14 days.

NOTE: any initial lab value below must be retested within 48 hours.

- Two sequential platelet counts <50,000/mm³. If the subject has a platelet count <25,000/mm³, investigational product should be temporarily withheld pending the confirmatory retest.
- Two sequential neutrophil counts <500/mm³.
- Two sequential lymphocyte counts <500/mm³.
- Two sequential hemoglobin assessments <8.0 g/dL or <30% from baseline value.
- Any of the following:
 - Two sequential AST or ALT elevations >3 times the upper limit of normal with at least one Total Bilirubin value >2 times the upper limit of normal.
 - Two sequential AST or ALT elevations >3 times the upper limit of normal with an abnormal INR.
 - Two sequential AST or ALT elevations >3 times the upper limit of normal accompanied by symptoms consistent with hepatic injury.
 - Two sequential AST or ALT elevations >5 times the upper limit of normal, regardless of Total Bilirubin or accompanying symptoms.

NOTE:

 Any of the above findings should prompt review of "The Potential Cases of Drug-Induced Liver Injury," Section 8.4.2 for which additional investigations must be conducted. • Two sequential increases in serum creatinine that are >50% over the average of screening and baseline values AND an absolute increase in serum creatinine ≥0.5 mg/dL. At the time of study completion or discontinuation, if a subject should exhibit elevations in serum creatinine ≥33% above the average of screening and baseline values, they will be re-tested every 1 to 2 weeks until the serum creatinine elevation is fully reversed to within 10% of the average of screening and baseline values or has stabilized.

Having met Discontinuation Criteria, the subject must be permanently withdrawn from treatment, have their end of treatment visit, and will then enter the 4-week follow-up period.

Additional individual subject safety monitoring, including laboratory testing or unscheduled study visits, in addition to these guidelines is at the discretion of the investigator and dependent on any perceived safety concerns. Unscheduled laboratory testing through the central laboratory may be obtained at any time during the study to assess such concerns.

If a subject has a clinically significant, treatment emergent, abnormality at the time of withdrawal from the study, the Pfizer medical monitor (or designee) should be notified and every effort should be made to arrange follow-up evaluations at appropriate intervals to document the course of the abnormality. All abnormal laboratory events of clinical significance should be followed until the laboratory values have returned to normal or baseline levels or are deemed clinically stable. Follow-up for abnormal laboratory findings and adverse events by the investigator is required until the event or its sequelae resolve or stabilize at a level acceptable to the investigator, and Pfizer concurs with that assessment.

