- Chest radiograph (or chest Computed Tomography (CT) scan, if available) taken at screening with changes suggestive of active tuberculosis (TB) infection as determined by a qualified radiologist. A chest X-ray is required, unless previously performed and documented within 12 weeks prior to Study Day 1.
- A history of either untreated or inadequately treated latent or active TB infection.
- A subject who is currently being treated for active TB infection is to be excluded.
- 19. ANY of the following abnormalities in clinical laboratory tests at screening, as assessed by the study-specific laboratory and confirmed by a single repeat, if deemed necessary:
 - Absolute neutrophil count of $<1.2 \times 10^9/L (<1200/mm^3)$;
 - Hemoglobin <10.0 g/dL or hematocrit <30%;
 - Platelet count of $<150 \times 10^9/L$ ($<150,000/mm^3$);
 - Absolute lymphocyte count of $< 0.50 \times 10^9 / L (< 500 / mm^3)$;

NOTE: In the Czech Republic only an Absolute lymphocyte count of $<0.75 \times 10^9$ /L (<750/mm³) is exclusionary.

- Estimated Creatinine Clearance <40 mL/min based on the age appropriate calculation, or serum creatinine >1.5 times the upper limit of normal (ULN);
- Aspartate aminotransferase (AST) or alanine aminotransferase (ALT) values >2 times the ULN;
- Total bilirubin ≥1.5 times the ULN; subjects with a history of Gilbert's syndrome may have a direct bilirubin measured and would be eligible for this study provided the direct bilirubin is ≤ ULN.
- 20. In the opinion of the investigator or sponsor, have any uncontrolled clinically significant laboratory abnormality that would affect interpretation of study data or the subject's participation in the study.
- 21. Have undergone significant trauma or major surgery within 1 month of the first dose of investigational product.

22. Investigator site staff members directly involved in the conduct of the study and their family members, site staff members otherwise supervised by the investigator, or subjects who are Pfizer employees, including their family members, directly involved in the conduct of the study.

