6.9.2. Laboratory Data

Laboratory data will be listed and summarized in accordance with the CaPS reporting standards. Summaries of subjects meeting pre-specified monitoring and discontinuation criteria will be created using methods for categorical data (see [Section 5.2.4](#)).

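### The relative part of the mandatory hemoglobin stopping rule in Protocol Appendix 4 does not state the threshold evidently meant, a fall of more than 30% from baseline

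*Protocol*

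**What the plan says.** Appendix 4 of the protocol has two tiers of laboratory rules.

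- **Monitoring tier (prompt retest).** The hemoglobin trigger is "Any single hemoglobin value <9.0 g/dL or one that drops ≥2 g/dL below baseline", with confirmation ideally within 3 to 5 days.
- **Discontinuation tier.** The stem is mandatory: "Subjects must be permanently discontinued from treatment if they meet any of the following criteria at any point in the study". The hemoglobin item under it is "Two sequential hemoglobin assessments <8.0 g/dL or <30% from baseline value". A note above the laboratory items in this tier asks for a retest of the initial value within 48 hours.

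The creatinine item in the same discontinuation list states both direction and reference: "Two sequential increases in serum creatinine that are >50% over the average of screening and baseline values".

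No other section of the protocol or SAP restates or corrects the hemoglobin item. SAP 6.9.2 relies on it without giving a threshold: "Summaries of subjects meeting pre-specified monitoring and discontinuation criteria will be created using methods for categorical data".

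**The concern.** A relative stopping rule needs a reference, a direction and a size. This one has the reference and a size, but no word such as decrease or below, and it uses a less-than sign where a rule about a large fall would use greater-than. The reader has to supply the rule.

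The item decides whether stopping treatment is compulsory. Hematopoietic effects are among the potential risks named in Protocol 1.4, so the rule is relevant to this drug. If the relative limb is disabled by a misreading, three things change for the affected values:

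- Permanent discontinuation becomes a matter of judgement.
- The retest falls back from 48 hours to the looser 3-to-5-day target.
- The count of subjects meeting discontinuation criteria under SAP 6.9.2 depends on which reading the programmer chose.

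**Working it through.** The plan gives no derived figure to reproduce, so the check is to apply each reading of the relative limb and compare it with the other hemoglobin rules.

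**Inputs from the documents**

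- Absolute stopping limit: 8.0 g/dL (Appendix 4, discontinuation criteria).
- Relative figure: 30%, referred to baseline (same item).
- Retest trigger: a drop of at least 2 g/dL below baseline (Appendix 4, monitoring criteria).
- Screening exclusion: hemoglobin below 10.0 g/dL (Protocol 4.2, criterion 19).

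**Assumption.** The documents give no hemoglobin distribution. Baselines *b* of 10 to 16 g/dL are used for illustration.

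**Reading A: change from baseline smaller than 30%.** At *b* = 14 the limb is met by any value between 0.7 × 14 = 9.8 and 1.3 × 14 = 18.2 g/dL. A value of 13.5 is a fall of 0.5/14 = 3.6% and meets it. A value of 8.5 is a fall of 5.5/14 = 39.3% and does not. The rule runs backwards, and context excludes it.

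**Reading B: value below 30% of baseline (Hb < 0.3*b*).** This acts before the 8.0 g/dL limit only if 0.3*b* > 8.0, that is *b* > 8.0/0.3 = 26.7 g/dL. Below that baseline the limb adds nothing.

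**Reading C: fall of more than 30% (Hb < 0.7*b*).** This adds to the 8.0 g/dL limit once 0.7*b* > 8.0, that is *b* > 8.0/0.7 = 11.4 g/dL. It also fits the two-tier structure: a 30% fall exceeds the 2 g/dL retest trigger whenever *b* > 2/0.3 = 6.7 g/dL, so the stopping tier is the more severe one.

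| Baseline (g/dL) | Retest at or below (*b* − 2) | B: 0.3*b* | C: 0.7*b* | Values stopped under C but not under B |
|---|---|---|---|---|
| 10 | 8.0 | 3.0 | 7.0 | none (8.0 limit acts first) |
| 11 | 9.0 | 3.3 | 7.7 | none (8.0 limit acts first) |
| 12 | 10.0 | 3.6 | 8.4 | 8.0 to <8.4 |
| 14 | 12.0 | 4.2 | 9.8 | 8.0 to <9.8 |
| 16 | 14.0 | 4.8 | 11.2 | 8.0 to <11.2 |

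The retest column shows only the relative trigger; the separate trigger below 9.0 g/dL also applies.

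Only reading C gives a relative limb that does any work and agrees with the retest rule.

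**The case against.** The best case for leaving the rule alone is that nobody would misread it. The platelet, neutrophil and lymphocyte items just before it, and the absolute hemoglobin limit in the same line, are all low-side limits written with a less-than sign, and the paired retest rule speaks of a drop. Reading B also needs *of* in place of *from*, and gives limits of 3.6 to 4.8 g/dL at baselines of 12 to 16, which a clinician would reject beside a limit of 8.0. A less-than sign would even be right for a signed change of −30%, so a minus sign may have been lost, in the source or in the reading of the PDF.

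Safeguards overlap as well. A value in the gap lies below 0.7*b* with *b* above 11.4, so it is a fall of more than 0.3 × 11.4 = 3.4 g/dL and triggers a retest. The investigator can interrupt dosing for up to 14 days and must stop treatment if restarting is not judged safe in that time. Sponsor clinicians review individual data (Protocol 7.3), and the external committee monitors safety (Protocol 9.4).

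Much of this stands. Many sites would infer the intent, no document shows that anyone adopted reading B, and a wrong SAP count is a possibility rather than a finding. The safeguards reduce the consequence. They do not make the written threshold correct: they leave to judgement what the stem makes compulsory. Extraction error cannot be excluded, but the greater-than signs in the neighboring liver and creatinine items came through intact. Correcting the sign alone would still leave the direction unstated.

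**Conclusion.** The concern holds. The relative limb is wrong as written: one literal reading is backwards, the other is inert at any baseline below 26.7 g/dL, and the only workable reading is not what the words say.

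The difference between the evident intent and reading B opens at a baseline of 11.4 g/dL and widens with baseline: 0.4 g/dL at 12, 1.8 at 14 and 3.2 at 16 (0.7*b* − 8.0). Those baselines are assumptions, so no number of subjects is estimated. The 10.0 g/dL entry limit applies at screening, not on Day 1, but this does not matter here because no gap exists below 11.4 g/dL.

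The effect is confined to whether stopping is mandatory, how fast the retest follows, and the SAP 6.9.2 count. Endpoints, sample size, power and type I error are not affected. The documents do not settle whether the limit should be more than 30% or at least 30%.

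**What to change.** Ask the sponsor to confirm the intent, including whether exactly 30% counts. Then replace the relative limb in Appendix 4 with: *or a decrease of >30% from baseline value*. Both the sign and the direction must change; inserting *decrease* while keeping the less-than sign would still describe small falls. The 8.0 g/dL limit and the retest triggers need no change.

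Use the same definition for the SAP 6.9.2 summary of subjects meeting discontinuation criteria.

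The cost is one line, by clarification letter or in the next amendment, and one matching programming note.
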